3.3 Follow Up Visit (Visit 3) Evaluations

The following procedures will be performed 21-30 days after randomization for the purpose of determining subject compliance; determining either presence or absence of the subject's baseline infection and whether or not additional treatment is needed; and obtaining information on concomitant medication use and possible adverse events.

If a subject was unable to return for Visit 2 but returns for Visit 3, available information that was to be obtained at Visit 2 regarding study drug administration/compliance and time to resolution/reoccurrence of symptoms may be obtained at Visit 3. The subject's diary should be reviewed and unused drug collected. Subjects in the Mixed Infection Study who missed Visit 2 should have hematology and chemistry labs obtained.

- Assessment of Compliance: Subjects are queried to determine compliance with study drug administration and study instructions.
- Subject Assessment of Symptoms: Subjects will be asked to rate their current vulvovaginal symptoms of itching, burning, and irritation as absent=0, mild=1, moderate=2, or severe=3. The sum of this symptom score will be added to the vulvovaginal signs score obtained during the pelvic examination to determine a combined symptom and sign severity score.
- Laboratory Tests and Specimen Collections: The lab tests listed below will be obtained at Visit 3.
 - Vaginal culture for Candida species
 - Vaginal Gram stain
- Pelvic Examination and Specimen Collections
 - Vulvovaginal signs rating
 - Vaginal discharge characterization
 - Vaginal pH measurement
 - KOH Whiff Test
 - Saline wet mount
 - Vaginal Candida culture
 - Vaginal Gram stain
- Assessment of Clinical Status, Need for Additional Treatment: Following subject evaluation, the investigator/clinician will be asked to document whether the subject requires any additional treatment for vaginal infection. Subjects who do require additional treatment should be treated per investigator/clinician judgment.
- Subject Satisfaction Survey: Subjects should be given the Subject Satisfaction Survey and asked to complete the form before leaving the clinic. Completion of the survey is voluntary and does not affect participation in the study in any way.

3.4 Limited Termination Visit

In instances where Visit 1 lab results make a subject ineligible for the study (i.e. subject randomized but did not meet inclusion/exclusion criteria), subjects should be terminated when exclusionary lab results become known. Procedures for these subjects are more limited but require a safety assessment including collection of adverse events, concomitant medications, and safety blood labs if the subject was enrolled in the Mixed Infection Study and safety labs were not already obtained at Visit 2. Subject diaries should be reviewed and unused drug tubes collected. Drug administration/compliance should be ascertained if not already done. Lab results that would make a subject ineligible are: positive gonorrhea, chlamydia, trichomonas, or herpes tests; normal Nugent score < 4 (for BV and Mixed Infection subjects); or negative *Candida* culture (for VVC and Mixed Infection subjects).

4. STATISTICAL METHODS

The following is a detailed proposal of the statistical summaries planned for subject data collected during the trial. Summary statistics of all important demographic, study conduct, efficacy, and safety data will be provided in tables. Case report form, clinical laboratory, and efficacy evaluation data will be provided in listings.

4.1 General Methods

Data from this study will be summarized with descriptive statistics. Descriptive summaries of baseline and demographic data will include frequency and percent relative frequency for categorical data; frequency and median for ordinal data; and frequency, mean, standard deviation, and minimum and maximum for quantitative data. In addition, 95% confidence intervals will be calculated, as appropriate. For scheduled measurements that are repeated out of schedule, such as repeat laboratory tests, the last measurement within a scheduled time interval (i.e. days 7 – 14 for Visit 2 and days 21 – 30 for Visit 3) will be used for data summaries. All results, whether scheduled or repeat, will be listed.

Each of the three infection studies within the trial will be analyzed separately.

The primary statistical objective of each infection study is listed below:

1. BV Study: Demonstrate the superiority of BV Gel (0.9% metronidazole gel) to Placebo Gel in the treatment of bacterial vaginosis (BV).
2. VVC Study: Demonstrate the superiority of VVC Gel (0.8% terconazole gel) to Placebo Gel in the treatment of vulvovaginal candidiasis (VVC).
5. Mixed Infection Study: Demonstrate the superiority of Combo Gel (0.9% metronidazole gel and 0.8% terconazole gel) to both single entity gels (BV Gel alone and VVC Gel alone).

4.2 Analysis Populations

The primary assessments of efficacy will be based on the modified intent-to-treat (mITT) population. In addition to the mITT analyses of the data, analyses will also be conducted on the per protocol (PP) population. The data analysis populations are defined as:

- ITT: The intent-to-treat population will include all subjects randomized to treatment.
- mITT: The modified intent-to-treat population will include all subjects randomized to treatment and administered at least one dose of study drug. Subjects who are Lost to Follow-up and for whom there is no documentation to ascertain whether or not they were administered treatment will be excluded from the mITT population.
 - In addition, to be included in the mITT population subjects in the VVC and Mixed Infection studies must have a positive baseline vaginal fungal culture for *Candida* species. Subjects in the BV and Mixed Infection studies must have a Gram stain Nugent score of ≥ 4 at the baseline visit.
 - Subjects randomized to treatment but whose baseline laboratory tests subsequently reveal positive results for *Trichomonas vaginalis*, *Chlamydia trachomatis*, and/or *Neisseria gonorrhoeae* will be excluded from the mITT population.
- PP: The per protocol population will include the subset of mITT subjects that had no major protocol violations and who are classified as efficacy evaluable with no missing data required to determine primary endpoints. Major protocol violations likely to bias assessment of the primary endpoint for the per protocol population will be determined prior to unblinding the data.
- Safety: The safety population will include all subjects randomized to treatment and administered at least one dose of study drug.

Major protocol deviations (i.e. deviations likely to bias assessment of the primary efficacy measure) that will be used to assess inclusion in the PP population will be determined and reviewed by the Sponsor prior to unblinding the data.

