3.1 Screening/Baseline Evaluations

Baseline (visit 1) medical evaluations will include:

- Medical and surgical history
- Contraceptive/obstetric status and gynecologic history
- Use of concomitant medications (i.e. current and within 30 days of enrollment) as well as treatments for BV and/or VVC infections within the past year
- Subject Assessment of Symptoms: Subjects will be asked to rate their current vulvovaginal symptoms of itching, burning, and irritation as absent=0, mild=1, moderate=2 or severe=3. The sum of the symptom score will be added to the vulvovaginal signs score obtained during the pelvic examination to determine a combined symptom and sign severity score.
- General physical examination and vital signs
- Laboratory tests
 - Urine pregnancy test for all women of child bearing potential
 - Papanicolaou smear (if subject is ≥ 21 years old and a Pap smear was not done within the past 3 years)
 - Tests for *Neisseria gonorrhoeae*, *Chlamydia trachomatis*, and *Trichomonas vaginalis*
 - Culture for *Herpes simplex* (only if suspected)
 - Vaginal culture for *Candida* species
 - Vaginal Gram stain

- CBC with differential and blood chemistries (i.e. BUN, Creatinine, ALT, AST, ALP, and bilirubin) for subjects enrolled in the Mixed Infection Study

Baseline (visit 1) pelvic examination and specimen collections will include:

- Visual inspection: rule out lesions caused by Herpes simplex virus or human papilloma virus (i.e. genital warts)
- Vulvovaginal signs rating: rate the degree of vulvovaginal edema, erythema, and excoriation as absent = 0, mild = 1, moderate = 2 or severe = 3. The sum of these ratings will be added to the vulvovaginal symptoms score given by the subject to determine a combined symptom and sign severity score. This total score must be > 2 in order to meet entry criteria for enrollment into the VVC or Mixed Infection study.
- Vaginal discharge characterization: By visual examination, characterize vaginal discharge in accordance with the descriptions below.
 - Normal/physiologic: normal discharge may vary in appearance and consistency depending on the menstrual cycle;
 - Abnormal: consistent with BV (i.e. off-white [milky or gray], thin, homogeneous discharge);
 - Abnormal: consistent with VVC (i.e. white, creamy, and curdy [cottage cheese like] adherent to the epithelium);
 - Abnormal: consistent with Mixed Infection (i.e. discharge of varying characteristics with relation to odor, color, and consistency)

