- pH measurement: Obtain a vaginal pH measurement with the pH indicator strips provided.
- KOH Whiff Test
- KOH and saline wet mounts
- Vaginal Candida culture: Obtain a Candida culture as specified in the central laboratory manual utilizing the collection and shipment supplies provided.
- Vaginal Gram Stain: Obtain a Gram Stain as specified in the central laboratory manual utilizing the collection and shipment supplies provided.
- Papanicolaou smear: Obtain a Pap smear if subject is ≥ 21 years old and has not had one within the past 3 years.
- Test for Neisseria gonorrhoeae, Chlamydia trachomatis, and Trichomonas vaginalis as specified in the central laboratory manual utilizing the collection and shipment supplies provided.
- Culture for Herpes simplex (only if suspected).

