4.6 Handling of Missing Data

By definition, all subjects in the PP population will have sufficient data required to determine primary endpoints. In instances where some (but not all) of the data is missing, two situations are possible: 1) some data are not available but the data that is available indicates for certain the patient is a failure, and 2) the data that is available indicates a possible cure and nothing indicates a failure, but without complete data it is not possible to determine for certain it is indeed a cure. Thus, a patient with situation 1) will be considered evaluable, while a patient with situation 2) will be non-evaluable and thus not included in the PP population. Any patients with all data missing will also be non-evaluable.

For subjects who are not eligible for inclusion in the PP populations but who are eligible for inclusion in the mITT subject populations, all missing data will be imputed as worst-case scenario outcome (e.g. failure).

If adverse event start dates are missing or incomplete, the following rules will apply for determining if an event is to be considered treatment emergent. If start date is completely missing, start date will be set as same day as start of treatment and assumed to be at a time following subject's first dose. If start date is incomplete, the date closest to start of treatment will be assumed, without compromising the incomplete data available for the start date.

If study medication start dates are missing or incomplete, the following rules will apply for determining inclusion in the Safety population. If the start date is completely missing and there is no documentation indicating that the patient used study medication, the date will be left as missing and the patient will be excluded from the Safety population. If the start date is completely missing or incomplete and there *is* documentation that indicates the patient used study medication, the date will be imputed to the earliest date and time post-randomization that is consistent with the partial data, and the patient will be included in the Safety population.

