4.7 Efficacy Analyses

4.7.1 Primary Efficacy Analysis

The primary efficacy endpoint is the cure rate at the test-of-cure visit (Visit 2). Definitions of cure for each of the three infection studies are provided in [Section 4.3](#).

Subjects in all studies will be categorized as cure or failure for the mITT analyses, and as cure, failure or non-evaluable for the PP analysis. The number and percentage of subjects in each treatment group in each of these categories will be reported. Separate statistical analyses will be performed for each of the three infection studies. All treatment comparisons will be based on two-tailed 0.05 significance level hypothesis tests and 95% confidence intervals for the difference in proportion of successes in each treatment. The primary comparison of treatment groups for each study will be performed using a continuity corrected Chi-squared test and Wald continuity corrected confidence intervals. It is anticipated that in some treatment groups in one or more of the infection studies, there may not be sufficient expected cell counts for the Chi-squared test and confidence intervals based on the normal approximation to be

accurate. Therefore, if all expected cell counts are not at least 5, Fisher's Exact test and confidence intervals using the method of Chan and Zhang (1999) will be used.

The primary efficacy analysis for each of the three infection studies will be performed using the mITT population with worst case scenario imputation for missing data. Supportive analyses will also be conducted using the PP population.

Efficacy analysis will not be done for the ITT population, as subjects in the BV and Mixed studies who do not have a gram stain ≥ 4 , or subjects in the VVC and Mixed studies who do not have a positive yeast culture, are not evaluated for efficacy. These subjects do not return for Visit 2; rather, they have the Limited Termination visit for safety evaluations only.

BV Study: The primary statistical objective of the BV infection study is to demonstrate the superiority of BV Gel to Placebo Gel in the treatment of BV. The assessment of superiority will be performed by conducting a continuity corrected Chi-squared test for a difference in the proportion of BV cure between the two treatments. Also, a 95% two-sided confidence interval for the difference in proportion of BV cure between the two treatments will be constructed.

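### The mITT exclusions in SAP 4.2 omit the positive herpes test that SAP 3.4 makes exclusionary; the effect is very small

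*SAP*

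**What the plan says.** SAP 3.4 (Limited Termination Visit) lists the Visit 1 results that disqualify a subject after randomisation: "Lab results that would make a subject ineligible are: positive gonorrhea, chlamydia, trichomonas, or herpes tests; normal Nugent score < 4" (BV and Mixed studies), or a negative Candida culture (VVC and Mixed studies). For all of them, "subjects should be terminated when exclusionary lab results become known". The limited visit collects safety, diary and dosing information and has no efficacy assessment.

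SAP 4.2 (Analysis Populations) defines the mITT as randomised, dosed subjects who meet the Nugent and/or Candida criterion of their study. It then removes three infections: "Subjects randomized to treatment but whose baseline laboratory tests subsequently reveal positive results for" trichomonas, chlamydia and/or gonorrhea. Herpes is not named.

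Under SAP 4.6, for subjects in the mITT but not in the PP population, "all missing data will be imputed as worst-case scenario outcome (e.g. failure"). SAP 4.7.1 makes the mITT analysis with this imputation the primary one.

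On how often herpes can arise, SAP 3.1 requires a visual inspection at Visit 1 to "rule out lesions caused by Herpes simplex virus or human papilloma virus", and the baseline test list reads "Culture for Herpes simplex (only if suspected").

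**The concern.** Two lists that should describe the same group differ by one item. A subject who is dosed, has confirmed baseline infection and then proves herpes-positive meets every mITT condition in 4.2. If 3.4 takes her out before Visit 2, she has no outcome, and 4.6 scores her as a failure. She then counts against her arm because the plan ended her participation, not because treatment failed. A subject with any other disqualifying laboratory result is simply left out. At stake is a slight dilution of the primary cure rates and an inconsistent rule that would have to be settled at data review.

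**Working it through.** **The two lists side by side**

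| Visit 1 result | Ineligible under 3.4 | Outside the mITT under 4.2 |
|---|---|---|
| Positive gonorrhea | yes | yes |
| Positive chlamydia | yes | yes |
| Positive trichomonas | yes | yes |
| Nugent score below 4 (BV, Mixed) | yes | yes |
| Negative Candida culture (VVC, Mixed) | yes | yes |
| Positive herpes | yes | **no** |

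**Inputs.** SAP 4.5 gives cure rates and evaluable subjects per arm: BV 0.50 v 0.20, 58; VVC 0.70 v 0.20, 50; Mixed 0.35 v 0.10 for each single gel, 63. SAP 4.7.1 gives the test: continuity-corrected chi-squared, or Fisher's exact if any expected count is below 5, two-sided 0.05. The SAP does not give the number of herpes-positive subjects; one or two per arm is an assumption.

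**Step 1: the plan's own power.** Exact enumeration of Fisher's test gives 90.6% (BV), 99.94% (VVC) and 90.6% (Mixed, per comparison), against the stated 90.0%, > 99.9% and 90%. The 4.7.1 test rule gives the same values to one decimal, so the inputs are sound.

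**Step 2: one imputed failure.** Adding one failure to an arm of N with cure rate p lowers the rate by p − pN/(N+1) = p/(N+1). The evaluable counts give the largest values. For a lower end, assume that 20% of the mITT is non-evaluable and all of these are failures. Then N becomes 62 (VVC), 72 (BV) and 79 (Mixed), and p falls in proportion; for VVC Gel p = 0.70 × 50/62 = 0.565.

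| Arm | Evaluable counts | With 20% extra failures |
|---|---|---|
| VVC Gel (VVC study) | 0.70/51 = 1.37 points | 0.90 |
| BV Gel (BV study) | 0.50/59 = 0.85 | 0.55 |
| Combo Gel | 0.35/64 = 0.55 | 0.35 |
| Placebo (VVC study) | 0.20/51 = 0.39 | 0.26 |
| Placebo (BV study) | 0.20/59 = 0.34 | 0.22 |
| Single gel (Mixed study) | 0.10/64 = 0.16 | 0.10 |

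**Step 3: the comparison.** Add k imputed failures to the evaluable counts and enumerate power again under the 4.7.1 rule. With k in each arm the difference is (p1 − p2) × n/(n + k); for BV with k = 2, 0.30 × 58/60 = 29.0 points. With k in the active arm only it is p1 × n/(n + k) − p2; for BV with k = 2, 0.50 × 58/60 − 0.20 = 28.3 points. Each cell gives the difference in points, then power.

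| Study | None | 1 in each arm | 2 in each arm | 1 active only | 2 active only |
|---|---|---|---|---|---|
| BV | 30.0; 90.6% | 29.5; 90.0% | 29.0; 90.0% | 29.2; 89.1% | 28.3; 87.9% |
| VVC | 50.0; 99.9% | 49.0; 99.9% | 48.1; 99.9% | 48.6; 99.9% | 47.3; 99.9% |
| Mixed (per comparison) | 25.0; 90.6% | 24.6; 90.6% | 24.2; 90.6% | 24.5; 89.5% | 23.9; 88.6% |

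The largest power loss is 90.6 − 87.9 = 2.7 points, in the BV study with both subjects in the active arm.

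**The case against.** Section 3.4 governs eligibility and termination, while 4.2 defines an analysis set; the SAP nowhere says that every laboratory-ineligible subject must leave the mITT. Keeping a randomised, dosed, infection-confirmed subject is a respectable default for a population of this type. The supportive PP analysis already leaves her out, since 4.6 treats a subject with all data missing as non-evaluable, and Tables 14.1.3 and 14.1.4 will show violations and unmet criteria. The point about size stands in full. The argument that retention is intended does not: 4.2 carries over every other item in 3.4, no reason is given for treating herpes differently, and retention would score a termination required by the plan as a treatment failure.

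Three stronger readings are tempting and should be resisted.

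- A reader might infer that every herpes-positive subject becomes an imputed failure. That applies only to those terminated before Visit 2. If the result arrives later, Visit 2 data may exist and no imputation is needed.
- A reader might cite 4.7.1, "These subjects do not return for Visit 2; rather, they have the Limited Termination visit for safety evaluations only", as covering herpes. That sentence concerns only subjects who fail the Gram stain or yeast culture criterion. Termination for herpes rests on 3.4 alone.
- A reader might extend the point to another exclusion in 4.2: "Subjects who are Lost to Follow-up and for whom there is no documentation to ascertain whether or not they were administered treatment". That rule is not an error. It agrees with the one-dose requirement and with the Safety population rule in 4.6.

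**Conclusion.** The inconsistency between 3.4 and 4.2 is real and minor. It concerns only subjects who are suspected of herpes, randomised and dosed anyway, later confirmed positive, and terminated before Visit 2. No direction of bias is expected, because the culture is a baseline specimen and does not depend on the assigned arm. The figures rest on the SAP's cure rates, on its evaluable counts standing in for the mITT, and on an assumed one or two subjects per arm. They show a blemish in the definition of the primary population, not a threat to any study's conclusion. The Mixed figures are for each comparison singly, although that study must win both.

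**What to change.** Before unblinding, add a positive baseline Herpes simplex test to the mITT exclusions in SAP 4.2, so that the list matches 3.4. The cost is a few words, with no new table or analysis. The change also drops any herpes-positive subject who does have Visit 2 data, which is how 4.2 already treats the other three infections. Because the criterion is a baseline result, the exclusion does not depend on treatment.

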4.3 Efficacy Endpoints and Evaluations

The primary and secondary endpoints are reflective of each of the infection studies within the protocol. These include:

Primary Endpoints

- BV Study: BV cure rate, with cure defined as normal/physiologic discharge, negative whiff test, and < 20% clue cells (i.e. clinical cure)
- VVC Study: VVC cure rate, with cure defined as resolution of all signs and symptoms attributable to VVC (i.e. clinical cure)
- Mixed Infection Study: Mixed Infection cure rate, with cure defined as BV cure (i.e. BV clinical cure) AND a VVC cure (i.e. VVC clinical cure)

Primary efficacy endpoint evaluations will occur at the test-of-cure Visit 2.

If a subject requires additional treatment for vaginal discomfort/symptoms (i.e. a BV subject requiring treatment for BV, a VVC subject requiring treatment for VVC or a Mixed Infection subject requiring treatment for BV and/or VVC) prior to or at Visit 2, the subject will be considered a treatment failure. These subjects will be evaluable for the modified intent-to-treat (mITT) and the per-protocol (PP) population analyses, providing all other evaluability criteria for these population groups have been met.

Additionally, if a subject self-medicates herself for vaginal discomfort/symptoms at any time prior to Visit 2, the subject will be considered a treatment failure. If this occurs, the subject will remain evaluable for the mITT analyses but will be non-evaluable for the PP analysis.

Secondary Endpoints

Note, for BV a Gram stain Nugent score cure will be defined as a score of < 4, i.e. 0 – 3.

- BV Study: BV clinical and Gram stain Nugent score combined cure rate, and Gram stain Nugent score cure rate alone; changes/improvements in Amsel criteria and Nugent scores; time to resolution of symptoms
 - In addition, cure rates over time will be explored
- VVC Study: VVC clinical and mycologic cure rates combined and mycologic cure alone; changes/improvements in signs and symptoms scores; eradication (or persistence) of individual fungal species; time to resolution of symptoms
- Mixed Infection Study: BV clinical and Gram stain Nugent score cure rates alone and combined; changes/improvements in Amsel criteria and Nugent scores; VVC clinical and mycologic cure rates alone and combined; changes/improvements in signs and symptoms scores; eradication or persistence of individual fungal species; time to resolution of symptoms

